## (5) New lesions

The appearance of new malignant lesions denotes disease progression; therefore, some comments on detection of new lesions are important. There are no specific criteria for the identification of new radiographic lesions; however, the finding of a new lesion should be unequivocal: i.e. not attributable to differences in scanning technique, change in imaging modality or findings thought to represent something other than tumour (for example, some 'new' bone lesions may be simply healing or flare of pre-existing lesions). This is particularly important when important when the patient's baseline lesions show complete response. For example, necrosis of a liver lesion may be reported on a CT scan report as a "new" cystic lesion, which it is not.

A lesion identified on a follow-up study in an anatomical location that was not scanned at baseline is considered a new lesion and will indicate disease progression. An example of this is the patient who has visceral disease at baseline and while on study has a CT or MRI brain ordered which reveals metastases. The patient's brain metastases are considered to be evidence of PD even if he/she did not have brain imaging at baseline.

If a new lesion is equivocal, for example because of its small size, continued therapy and followup evaluation will clarify if it represents truly new disease. If repeat scans confirm there is definitely a new lesion, then progression should be declared using the date of the initial scan.

While FDG-PET assessments need additional study, it is reasonable to incorporate the use of FDG-PET scanning to complement CT scanning in assessment of progression (particularly possible 'new' disease). New lesions on the basis of FDG-PET imaging can be identified according to the following algorithm:

- a. Negative FDG-PET at baseline, with a positive FDG-PET at follow-up is a sign of PD based on a new lesion.
- b. No FDG-PET at baseline and a positive FDG-PET at follow- up:

If the positive FDG-PET at follow-up corresponds to a new site of disease confirmed by CT, this is PD.

If the positive FDG-PET at follow-up is not confirmed as a new site of disease on CT, additional follow-up CT scans are needed to determine if there is truly progression occurring at that site (if so, the date of PD will be the date of the initial abnormal FDG-PET scan).

If the positive FDG-PET at follow-up corresponds to a pre-existing site of disease on CT that is not progressing on the basis of the anatomic images, this is not PD.

## 4. Evaluation of best overall response

The best overall response is the best response recorded from the start of the study treatment until the end of treatment taking into account any requirement for confirmation. On occasion a response may not be documented until after the end of therapy so protocols should be clear if post-treatment assessments are to be considered in determination of best overall response. Protocols must specify how any new therapy introduced before progression will affect best response designation. The patient's best overall response assignment will depend on the findings of both target and non-target disease and will also take into consideration the appearance of new lesions. Furthermore, depending on the nature of the study and the protocol requirements, it may also require confirmatory measurement. Specifically, in non-randomised trials where response is the primary endpoint, confirmation of PR or CR is needed to deem either one the 'best overall response'. This is described further below.

## (1) Time point response

It is assumed that at each protocol specified time point, a response assessment occurs. Table 4 provides a summary of the overall response status calculation at each time point for patients who have measurable disease at baseline.

When patients have non-measurable (non-target) disease only, Table 5 is to be used.

Table 4 Time point response: patients with target (+/- non-target) disease

Target lesions	Non-target lesions	New lesions	Overall response
CR	CR	No	CR
CR	Non-CR/non-PD	No	PR
CR	Not evaluated	No	PR
PR	Non-PD or not evaluated	No	PR
SD	Non-PD or not evaluated	No	PD
Not evaluated	Non-PD	No	Non-evaluable

Target lesions	Non-target lesions	New lesions	Overall response
PD	Any	Yes or No	PD
Any	PD	Yes or No	PD
Any	Any	Yes	PD

**Abbreviation:** CR = complete response; PR = partial response; SD = stable disease.

Table 5 Time point response: patients with non-target disease only

Non-target lesions	New lesions	Overall response
CR	No	CR
Non-CR/non-PD	No	Non-CR/non-PD a
Not evaluated	No	Non-evaluable
Definite disease progression	Yes or No	PD
Any	Yes	PD

**Abbreviation:** CR = complete response; SD = stable disease.

**Note:** 'Non-CR/non-PD' is preferred over 'stable disease' for non-target disease since SD is increasingly used as endpoint for assessment in some trials so to assign this category when no lesions can be measured is not advised.

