#### **Criteria for study treatment discontinuation (whichever occurs first):**

- Subject has disease progression, unless the investigator believes the subject can still benefit from the study treatment clinically.
- The investigator determines that the subject cannot clinically benefit from the study treatment and continued study treatment may pose an unacceptable risk to the subject.
- There is major protocol deviation. After enrollment, the subject is found to be non-compliant with enrollment criteria in the study protocol or does not follow requirements in the study protocol, and the investigator believes that continued study treatment may pose an unacceptable risk to the subject.
- The subject has a poor compliance, uses prohibited concomitant medications without permission or fails to attend visits on schedule, which affects the evaluation of efficacy and/or safety, and the subject is considered inappropriate to continue the study at the discretion of the investigator.
- The subject experiences a particular comorbidity or complication, which, in the discretion of the investigator, makes it inappropriate to continue the study treatment.
- The subject experiences an intolerable toxicity.

- Subject pregnancy.
- Subject is lost to follow-up for more than 8 weeks.
- Subject death.
- Any other conditions in which the investigator believes that the study should be terminated.
- The subject refuses to continue the study treatment.
- The study site is closed prematurely, the study is prematurely terminated or the study ends.

Notes: After study treatment discontinuation, subjects will enter into the follow-up period (unless follow-up is not applicable).

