- 2) If a subject received a CT/MRI or other radiological examinations within 4 weeks prior to the first dose and has not received any anti-tumor therapy since this tumor assessment, and at the investigator's discretion, the tumor assessment can be performed according to RECIST v1.1, this examination result can be used as baseline tumor assessment result (repeated examination is not necessary).
- 3) A tumor assessment will be performed at the end of Cycle 1, for which the time window is the end of the cycle ± 1 day. Thereafter, tumor assessments will be performed once every 2 cycles, for which the time window is the end of every 2 cycles ± 7 days [if a subject's assessment result is CR, PR or stable disease (SD), the subject can continue the treatment and continue to receive tumor assessments once every 2 cycles].
- 4) The radiological confirmation examination of CR or PR should be completed 4-8 weeks after the first evaluation of CR or PR.
- 5) For the end of treatment visit (EOT), the investigator will determine whether a tumor assessment is required according to the actual condition. If a tumor assessment has been performed within 2 months prior to EOT, it is not necessary to repeat the tumor assessment at EOT visit.
- 6) During the subsequent follow-up visits once every 8 weeks (±7 days) after the last dose, a tumor assessment will be performed for the subjects who are assessed as having no tumor progression in the previous assessment.

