# 10.4.8 Efficacy analyses

- **ORR:** The proportion of patients with a best overall response of CR and PR as assessed per RECIST v1.1 in all patients.
- **DCR:** The proportion of patients with a best overall response of CR, PR and SD (duration ≥12 weeks) as assessed per RECIST v1.1 in all patients.
- **DOR:** The duration from the firstly documented CR or PR to the date of confirmed objective tumor progression (based on RECIST v1.1) or death for the subjects with a best overall response of CR or PR. For the patients who have no objective tumor progression or death at the end of trial, the date of the last objective tumor assessment will be taken as the censored date of DOR.
- **PFS:** The duration from the first dose of study drug to objective tumor progression (based on RECIST v1.1) or death. For the patients who have no objective tumor progression or death at the end of trial, the date of the last objective tumor assessment will be taken as the censored date of PFS.
- **OS:** The duration from the first dose of study drug to death. For patients who are alive at the end of trial, their last date known to be alive will be used as the censored date of OS.

Point estimates of ORR and DCR and their two-sided 95%CI will be calculated. The two-sided 95% CI of ORR and DCR are calculated based on the Clopper-Pearson method. Meanwhile, the number and percentage of subjects with CR, PR, SD and disease progression will be presented.

For DOR (for subjects experiencing CR and/or PR only), PFS and OS, Kaplan-Meier method will be adopted to calculate the median, lower quartile, upper quartile and two-sided 95% CI, and survival curves will be drawn.

For ORR, the estimated objective is shown in the table below.

Estimated objective:		
Population:	FGF19 or FGFR4 positive advanced primary HCC or other advanced solid	
	tumors	
Treatment:	See Section 6 for details	
Endpoint:	ORR	
Intercurrent events and handling strategies:	Discontinuation of study treatment or initiation of new anticancer therapy prior to CR or PR will be handled according to the while-on-treatment strategy.	
Summary at the population level:	ORR and corresponding two-sided 95%CI (estimated by Clopper-Pearson method) will be calculated	

For DOR, the estimated objective is shown in the table below.

Estimated objective:		
Population:	FGF19 or FGFR4 positive advanced primary HCC or other advanced solid	
	tumors	
Treatment:	See Section 6 for details	
Endpoint:	DOR	

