## (1) Evaluation of target lesions

• Complete Response (CR): Disappearance of all target lesions. Any pathological lymph nodes (whether target or non-target) must have reduction in short axis to <10 mm.

• Partial Response (PR): At least a 30% decrease in the sum of diameters of target lesions, taking as reference the baseline sum diameters.

- **Progressive Disease (PD):** At least a 20% increase in the sum of diameters of target lesions, taking as reference the smallest sum on study (this includes the baseline sum). In addition to the relative increase of 20%, the sum must also demonstrate an absolute increase of at least 5 mm. (Note: the appearance of one or more new lesions is also considered progression).
- **Stable Disease (SD):** Neither sufficient shrinkage to qualify for PR nor sufficient increase to qualify for PD, taking as reference the smallest sumdiameters while on study.

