#### (3) Best overall response: all time points

The best overall response is determined once all the data for the patient is known.

Best response determination in trials where confirmation of complete or partial response IS NOT required: Best response in these trials is defined as the best response across all time points (for example, a patient who has SD at first assessment, PR at second assessment, and PD on last

assessment has a best overall response of PR). When SD is believed to be best response, it must also meet the protocol specified minimum time from baseline. If the minimum time is not met when SD is otherwise the best time point response, the patient's best response depends on the subsequent assessments. For example, a patient who has SD at first assessment, PD at second and does not meet minimum duration for SD, will have a best response of PD. The same patient lost to follow-up after the first SD assessment would be considered inevaluable.

Best response determination in trials where confirmation of complete or partial response IS required: Complete or partial responses may be claimed only if the criteria for each are met at a subsequent time point as specified in the protocol. In this circumstance, the best overall response can be interpreted as in Table 6.

Table 6 Best overall response when confirmation of CR and PR required

Overall response First time point	Overall response Subsequent time point	BEST overall response
CR	CR	CR
CR	PR	SD, PD or PR a
CR	SD	SD provided minimum criteria for SD duration met, otherwise, PD
CR	PD	SD provided minimum criteria for SD duration met, otherwise, PD
CR	Non-evaluable	SD provided minimum criteria for SD duration met, otherwise, NE
PR	CR	PR
PR	PR	PR
PR	SD	SD
PR	PD	SD provided minimum criteria for SD duration met, otherwise, PD
PR	Non-evaluable	SD provided minimum criteria for SD duration met, otherwise, NE
Non-evaluable	Non-evaluable	Non-evaluable

**Abbreviation:** CR = complete response; PR = partial response; SD = stable disease.

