## 6. Confirmatory measurement/duration of response (DOR)

#### (1) Confirmation

In non-randomised trials where response is the primary endpoint, confirmation of PR and CR is required to ensure responses identified are not the result of measurement error. This will also permit appropriate interpretation of results in the context of historical data where response has traditionally required confirmation in such trials (see the paper by Bogaerts et al. in this Special Issue). However, in all other circumstances i.e. in randomised trials (phase II or III) or studies where stable disease or disease progression are the primary endpoints, confirmation of response is not required since it will not add value to the interpretation of trial results. However, elimination of the requirement for response confirmation may increase the importance of central review to protect against bias, in particular in studies which are not blinded.

In the case of SD, measurements must have met the SD criteria at least once after study entry at a minimum interval (in general not less than 6-8 weeks) that is defined in the study protocol.

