## (3) Duration of stable disease

Stable disease is measured from the start of the treatment (in randomised trials, from date of randomisation) until the criteria for progression are met, taking as reference the smallest sum on study (if the baseline sum is the smallest, this is the reference for calculation of PD).

The clinical relevance of the duration of stable disease varies in different studies and diseases. If the proportion of patients achieving stable disease for a minimum period of time is an endpoint of importance in a particular trial, the protocol should specify the minimal time interval required between two measurements for determination of stable disease.

Note: The duration of response and stable disease as well as the progression-free survival are influenced by the frequency of follow-up after baseline evaluation. It is not in the scope of RECIST to define a standard follow-up frequency. The frequency should take into account many parameters including disease types and stages, treatment periodicity and standard practice. However, these limitations of the precision of the measured endpoint should be taken into account if comparisons between trials are to be made.

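### Appendix I, Table 4 scores stable target lesions as overall PD, so SD cannot occur as a time-point response; applied as printed, it would distort DCR and PFS

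*Protocol*

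**What the plan says.** Appendix I, II.4(1) presents Table 4 as the calculation of overall response at each time point for patients with measurable disease at baseline. The row in question is "SD Non-PD or not evaluated No PD", in the column order target lesions, non-target lesions, new lesions, overall response.

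Elsewhere the protocol treats SD as a separate outcome that is not progression:

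- Appendix I, II.3(1) defines SD as "Neither sufficient shrinkage to qualify for PR nor sufficient increase to qualify for PD".
- II.4(3) uses SD as a time-point result, for example "a patient who has SD at first assessment, PR at second assessment". Table 6 in the same section takes SD as an input in two rows.
- II.6(1) requires that "measurements must have met the SD criteria at least once after study entry at a minimum interval", and II.6(3) lets SD run "until the criteria for progression are met, taking as reference the smallest sum on study".
- Section 10.4.8 defines DCR as the proportion with a "best overall response of CR, PR and SD (duration ≥12 weeks) as assessed per RECIST v1.1 in all patients".
- Section 4.3 (Tumor assessment) says that "if a subject's assessment result is CR, PR or stable disease (SD), the subject can continue the treatment" and go on with two-cycle scans.

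**The concern.** Table 4 is an operative table. Appendix I, II.4(4) refers to Tables 4 to 6 for determining objective response status. Inclusion criterion 3 (section 3.1) requires a measurable lesion in the expansion trial, so Table 4 applies to every expansion subject. Section 7.2 lists ORR, DCR, DOR, PFS and OS as expansion primary endpoints.

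If a response derivation, eCRF check or reader guide were built from the printed cell:

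- DCR would lose the subjects whose best finding is SD.
- PFS would record an event for a stable subject at the first post-baseline scan.
- DOR would end early for a responder whose target status moves back to SD without progressing.
- The same scan would meet the discontinuation criterion in section 3.3 ("Subject has disease progression, unless the investigator believes the subject can still benefit from the study treatment clinically") and also, on the SD definition, the continuation rule in section 4.3.
- ORR could be affected only indirectly, if a subject wrongly scored PD stopped treatment or post-treatment scanning before a later response.

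**Working it through.** The protocol states no design figure for this point, so the check is an enumeration of the table followed by a sizing of the effect.

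**1. Outputs of Table 4 as printed (nine rows).** CR 1, PR 3, PD 4, non-evaluable 1, SD 0. The sum is 1 + 3 + 4 + 1 + 0 = 9. The table's footnote expands the abbreviation SD, yet no row returns it.

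**2. A worked lesion example (hypothetical sizes, no new lesion, no non-target progression).** Take a baseline target sum of 50 mm.

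- Follow-up 35 mm: (35 − 50)/50 = −30%, which is PR under II.3(1) and PR in Table 4.
- Follow-up 36 mm: (36 − 50)/50 = −28%, which is SD under II.3(1) and PD in Table 4.

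Target PD requires an increase of at least 20% and at least 5 mm over the smallest sum, so a 28% shrinkage cannot be progression. II.3(4) also says that overall progression resting only on non-target change, with target SD or PR, will be extremely rare. The printed row makes PD automatic whenever target lesions are stable.

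**3. What remains of SD through Table 6.** Seven of its 11 rows can give a best response of SD: CR then PR, SD, PD or NE, and PR then SD, PD or NE. All seven start from a CR or PR. So, on the printed Table 4, SD as a best response survives only for some subjects with an unconfirmed CR or PR. A subject who is stable at every scan is scored PD at every scan and leaves DCR.

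**4. PFS timing.** The first scan is at the end of Cycle 1 (±1 day).

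- Expansion: C1D21 is study day 21.
- Escalation: if C1D1 falls on about D6 after the single dose and 5-day washout, C1D21 is about day 5 + 21 = 26.

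**5. Size of the DCR effect, illustration only.** Section 1.7 gives response counts for one similar drug. Suppose every disease-control case that is not a responder is SD and is recoded to PD:

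| Group | ORR | DCR reported | Non-responders within DCR | DCR after recoding |
|---|---|---|---|---|
| Phase I monotherapy | 4/74 | 34/74 = 45.9% | 34 − 4 = 30 (88%) | 4/74 = 5.4% |
| Phase II cohort 1 | 2/30 | 13/30 = 43.3% | 13 − 2 = 11 (85%) | 2/30 = 6.7% |
| Phase II cohort 2 | 2/36 | 22/36 = 61.1% | 22 − 2 = 20 (91%) | 2/36 = 5.6% |
| Phase II cohort 3 | 0/20 | 6/20 = 30.0% | 6 − 0 = 6 (100%) | 0/20 = 0% |

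On the planned expansion group size of 12 (section 4.1.2), take 1 confirmed PR, 4 SD of at least 12 weeks and 7 PD, with Clopper-Pearson limits as in section 10.4.8:

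- Row read as SD: (1 + 4)/12 = 41.7% (95% CI 15.2% to 72.3%).
- Row as printed: 1/12 = 8.3% (95% CI 0.2% to 38.5%).

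**The case against.** The strongest reply is that this is a one-letter slip with an obvious correction. The SD and PD definitions, the DCR definition and the continuation rule are all right, and section 10.4.8 cites RECIST v1.1, not Table 4. Nothing in the protocol says that a derivation is built from this table. The study is descriptive, and an experienced RECIST reader would override the cell. This stands as far as likelihood goes: the harm is conditional. It does not make the table right. The appendix itself points to Tables 4 to 6 for response status, and Table 4 covers every expansion subject.

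A text-extraction error in a single letter cannot be fully excluded. The other eight rows read cleanly, and a look at the printed page settles it.

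Several limits on the size are fair:

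- DCR would not fall exactly to ORR, because Table 6 still allows SD after an unconfirmed CR or PR.
- The Table 6 count is the same after the correction. A CR or PR followed by SD would be read as CR or PR followed by PD, which can still give SD if the minimum duration is met. The loss therefore falls on subjects who never reach CR or PR.
- The similar-drug figures come from another compound, with no stated minimum SD duration against 12 weeks here, so they are nearer a worst case than an estimate.
- The clash with the discontinuation criterion is partial, since that criterion has an investigator exception.
- Escalation subjects with non-target disease only use Table 5 and are unaffected.

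**Conclusion.** The concern holds: the Table 4 row is wrong as written. No reading reconciles an overall PD with target lesions that by definition have not progressed, no non-target progression and no new lesion.

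The consequence depends on literal use of the cell. In that case two expansion primary endpoints, DCR and PFS, are directly misclassified, and DOR is exposed as well. The drop in DCR depends on how much of disease control is SD. In the similar-drug data that share is 85% to 100%, assuming that all non-responding disease-control cases were SD without an unconfirmed response.

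**What to change.** In Appendix I, Table 4, change the overall response in the row for target SD, non-target non-PD or not evaluated and no new lesions from PD to SD. The protocol's own definitions fix that value, so no new response rule is being chosen. Then confirm that any eCRF edit check, reader guide or response-derivation specification returns SD for that combination. The cost is one cell and that check; there is no downside for the design or the analysis.

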## (2) Missing assessments and inevaluable designation

When no imaging/measurement is done at all at a particular time point, the patient is not evaluable (NE) at that time point. If only a subset of lesion measurements are made at an assessment, usually the case is also considered NE at that time point, unless a convincing argument can be made that the contribution of the individual missing lesion(s) would not change the assigned time point response. This would be most likely to happen in the case of SD. For example, if a patient had a baseline sum of 50 mm with three measured lesions and at follow-up only two lesions were assessed, but those gave a sum of 80 mm, the patient will have achieved PD status, regardless of the contribution of the missing lesion.

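### The missing-lesion rule in Appendix I names SD, but its own example and the response thresholds support only PD

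*Protocol*

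**What the plan says.** Protocol Appendix I, II.4(2), deals with scans on which only a subset of lesions was measured: "usually the case is also considered NE at that time point, unless a convincing argument can be made" that the missing lesion or lesions would leave the assigned response unchanged. The next sentence names the category in which this is expected: "This would be most likely to happen in the case of SD". An example follows: "if a patient had a baseline sum of 50 mm with three measured lesions and at follow-up only two lesions were assessed", and "those gave a sum of 80 mm, the patient will have achieved PD status, regardless of the contribution of the missing lesion".

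The thresholds stand in II.3(1), Evaluation of target lesions. PD is "At least a 20% increase in the sum of diameters of target lesions, taking as reference the smallest sum on study", and in addition "the sum must also demonstrate an absolute increase of at least 5 mm". PR needs a fall of at least 30% from the baseline sum. SD is whatever lies between the two.

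The Appendix is the working response standard for the trial. Section 3.1, criterion (3), refers to it for RECIST v1.1, and Section 10.4.8 assesses ORR and DCR by RECIST v1.1. DCR is defined there as "The proportion of patients with a best overall response of CR, PR and SD", with SD required to last at least 12 weeks. PFS without an event is censored at the last objective tumour assessment. Section 7.2 lists DCR and PFS among the primary endpoints of the expansion trial.

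**The concern.** The sentence and its example name different categories, so one of them must be wrong. An assessor with an incomplete scan who takes the sentence at face value is told that SD is the typical case in which the NE default may be set aside. SD counts towards disease control if it lasts long enough, and NE does not. If an incomplete scan is accepted as SD when the unmeasured lesion has in fact grown, progression goes unrecorded at that visit. The endpoints concerned are primary in expansion groups of 12 subjects (Section 4.1.2), where one subject's classification is visible in the result.

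**Working it through.** **Inputs.** Baseline sum 50 mm, three lesions, two measured at follow-up with a subtotal of 80 mm (the example in II.4(2)). PD, PR and SD thresholds from II.3(1). One assumption is added: the smallest sum on study equals the baseline, 50 mm.

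**Set-up.** Let S be the subtotal of the measured target lesions and m the diameter of the missing one. A diameter cannot be negative, so m ≥ 0 and the true sum is S + m ≥ S.

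- PD if S + m ≥ max(1.2 × smallest sum, smallest sum + 5) = max(60, 55) = 60 mm.
- PR if S + m ≤ 0.7 × baseline = 35 mm (CR if nothing remains).
- SD if S + m lies above 35 mm and below 60 mm.

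**The protocol's own example.** S = 80 mm is 30 mm above 50 mm, and 80/50 − 1 = 60%. It passes the 60 mm threshold even with m = 0, so the result is PD, as stated. A smaller reference sum lowers the threshold (48 mm for 40 mm, 36 mm for 30 mm), so PD holds for any smallest sum up to 50 mm. The example is correct.

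**Which category a partial sum can settle.** Classifying every whole-millimetre S from 0 to 120 mm over m from 0 to 300 mm gives:

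| Measured subtotal S | Categories still possible |
|---|---|
| 60 mm or more | PD only |
| 36 to 59 mm | SD or PD |
| 1 to 35 mm | PR, SD or PD |
| 0 mm | CR, PR, SD or PD |

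PD has a lower bound only, so adding an unknown non-negative length cannot undo it. SD is bounded on both sides, so the unknown length can always push the sum through the upper bound. For an apparent SD the condition is m < 60 − S:

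- S = 40 mm: SD only if m < 20 mm.
- S = 50 mm: SD only if m < 10 mm.
- S = 55 mm: SD only if m < 5 mm.

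No subtotal settles SD, PR or CR whatever the missing lesion measures. The wrong word is SD, and the example is right.

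**Where it could reach an endpoint.** Section 4.3 schedules scans at the end of Cycle 1 and then every two 21-day cycles: about weeks 3, 3 + 6 = 9 and 9 + 6 = 15 in the expansion trial. An SD-or-NE call near week 15 can decide whether the 12-week requirement is met. One subject in a group of 12 is 1/12 = 8.3 percentage points of DCR. With assumed counts, 4/12 = 33.3% (Clopper-Pearson 95% CI 9.9 to 65.1) would become 5/12 = 41.7% (15.2 to 72.3). This shows what one subject is worth and does not estimate how often it would happen.

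**The case against.** The strongest reply is that the sentence is commentary and the rule precedes it. The rule makes NE the default and asks for a convincing argument. Applied strictly, it returns NE for every apparent SD, because no apparent SD is certain. An assessor also sees the PD example. This stands: nothing in II.4(2) instructs anyone to score incomplete scans as SD.

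A reader might infer that DCR and PFS are therefore inflated. The documents do not support that.

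- **Direction.** The Table 4 row for target SD, with non-target disease not progressing or not evaluated and no new lesion, prints overall PD. Read literally, that lowers DCR and shortens PFS, so the net direction is open.
- **DCR.** Only SD of at least 12 weeks counts. An NE scan between adequate SD scans need not remove a subject's SD.
- **PFS.** Later censoring is not in itself a bias in a Kaplan-Meier estimate. Where PD is recorded at a later scan, the event date is the same whether the partial scan was called SD or NE. The two calls differ mainly when the partial scan is the subject's last, and Section 10.4.8 does not say whether an NE scan counts as the last objective assessment.
- **Scope.** II.4(4), Special notes on response assessment, leaves the handling of missing assessments to the analysis plan, which is not at hand. II.4(2) may therefore not be the only rule that applies.

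It could also be argued that SD is tenable if growth of the missing lesion is taken to be limited. For some sums that is so, but it rests on an added assumption and is not a result that holds whatever the missing lesion measures.

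None of this makes the sentence agree with its example or with the thresholds.

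**Conclusion.** The contradiction is certain and can be shown from the protocol alone: II.4(2) names SD, while its example and the II.3(1) thresholds support PD only. The result needs nothing beyond a missing diameter being zero or more. The 60 mm boundary is specific to a baseline and smallest sum of 50 mm, but the ordering is general.

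The consequence is a possibility. The sentence may lead assessors to accept SD where NE should stand, which could wrongly support qualifying SD in DCR or, on a last partial scan, move PFS censoring later. The frequency of partly measured scans is not given, so the size of the effect cannot be derived; 8.3 points per subject in a group of 12 is only the unit. Because the Appendix defines response for primary expansion endpoints, the wording should be corrected, though nothing suggests that the design or planned analyses fail because of it.

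**What to change.** In Appendix I, II.4(2), change SD to PD in the sentence that names the likely category. Keep NE as the default for a partly measured time point and keep the requirement for a convincing argument. A blanket bar on assigning SD, PR or CR from any partial set would go further than the error requires.

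At the same time reconcile the Table 4 row that gives overall PD for target SD with non-PD non-target disease and no new lesions. As printed it leaves no route to an overall SD for patients with target disease, although DCR counts SD. Correcting one place without the other would leave SD and PD inconsistent within the same Appendix.

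The cost is a wording edit. No new data, visits or design change are needed. A few time points that might have been called SD would be NE.
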